7.1.3 Dose Schedule for BMS-986213 or Nivolumab Plus FOLFOX

- Participants assigned to FOLFOX will receive BMS-986213 (relatlimab 160 mg/nivolumab 480 mg) or nivolumab 480 mg, administered IV over 60 minutes or 30 minutes, respectively, on Days 1 and 29 of every odd-numbered 6-week treatment cycle (Cycle 1, 3, 5, etc) and Day 15 of every even numbered 6-week treatment cycle (Cycle 2, 4, 6, etc). Oxaliplatin 85 mg/m², leucovorin 400 mg/m², and fluorouracil 400 mg/m² will be administered IV on Days 1, 15, and 29 of each 6-week treatment cycle, and fluorouracil 1200 mg/m² IV continuous infusion over 24 hours daily (or per local standard) on Days 1 and 2, 15 and 16, and 29 and 30 of each 6-week treatment cycle (see Table 7.1.3-1). As a consequence of this dosing regimen, FOLFOX will be administered alone, without immunotherapy, on Day 15 of each odd numbered 6-week

treatment cycle and Days 1 and 29 of each even numbered 6-week treatment cycle. Immunotherapy treatment should be administered first, prior to chemotherapy treatment. Dosing windows for subsequent FOLFOX doses should adhere to recommendations in the prescribing information or local standards, where indicated.

Premedication for potential infusion reaction is not recommended for the first dose of either treatment. Premedication may be administered for nausea and vomiting prophylaxis, after the completion of the immunotherapy treatment or, in the absence of preceding immunotherapy, before chemotherapy administration, as clinical presentation warrants and per local standard.

Table 7.1.3-1: Dose Schedule for BMS-986213 or Nivolumab Plus FOLFOX

Treatment Group	Drug Name	Cycle 1 (Week 1)	Cycle 2 (Week 7)	Cycle 3 (Week 13)	Cycle 4 (Week 19)	Odd Cycles Starting at Cycle 5 (Week 25) until EOT	Even Cycles Starting at Cycle 6 (Week 31) until EOT
BMS-986213 or nivolumab in combination with FOLFOX	BMS-986213 (relatlimab 160 mg/nivolumab 480 mg), or nivolumab 480 mg,	Days 1 and 29	Day 15	Days 1 and 29	Day 15	Days 1 and 29	Day 15
	Oxaliplatin 85 mg/m ²	Days 1, 15, 29	Days 1, 15, 29	Days 1, 15, 29	Days 1, 15, 29	Days 1, 15, 29	Days 1, 15, 29
	Leucovorin 400 mg/m ²	Days 1, 15, 29	Days 1, 15, 29	Days 1, 15, 29	Days 1, 15, 29	Days 1, 15, 29	Days 1, 15, 29
	Fluorouracil 400 mg/m ²	Days 1, 15, 29	Days 1, 15, 29	Days 1, 15, 29	Days 1, 15, 29	Days 1, 15, 29	Days 1, 15, 29
	Fluorouracil 1200 mg/m ²	Days 1 & 2, 15 & 16, 29 & 30	Days 1 & 2, 15 & 16, 29 & 30	Days 1 & 2, 15 & 16, 29 & 30	Days 1 & 2, 15 & 16, 29 & 30	Days 1 & 2, 15 & 16, 29 & 30	Days 1 & 2, 15 & 16, 29 & 30

7.1.4 Dose Schedule for BMS-986213 or Nivolumab Plus SOX

Participants assigned to SOX will receive BMS-986213 (relatlimab 120 mg/nivolumab 360 mg) or nivolumab 360 mg, administered IV over 60 or 30 minutes, respectively, and oxaliplatin 130 mg/m² administered IV on Days 1 and 22 of each 6-week treatment cycle, and oral S-1 twice daily (ie, 1 dose in the morning and 1 dose in the evening) on Days 1 to 14 and Days 22 to 35 of each 6-week treatment cycle. S-1 (tegafur/gimeracil/oteracil) dose should be administered as calculated according to body surface area (BSA, mg/m²/dose): BSA < 1.25 m², 40 mg/dose; ≥ 1.25 and < 1.5 m², 50 mg/dose; ≥ 1.5 m², 60 mg/dose (see Table 7.1.4-1). Immunotherapy treatment should be administered first, prior to chemotherapy treatment. Dosing windows for subsequent SOX doses should adhere to recommendations in the prescribing information or local standards, where indicated.

Premedication for potential infusion reaction is not recommended for the first dose of either treatment. Premedication maybe administered for nausea and vomiting prophylaxis, after the completion of the immunotherapy treatment or, in the absence of preceding immunotherapy, before chemotherapy administration, as clinical presentation warrants and per local standard.

Participants should be provided with drug diaries at each visit and instructed to record intake of S-1 in the diary after each twice daily administration.

Table 7.1.4-1 Dose Schedule for BMS-986213 or Nivolumab Plus SOX

Treatment Group	Drug Name	Cycle 1 (Week 1)	Cycle 2 (Week 7)	Cycle 3 (Week 13)	Cycle 4 (Week 19)	Cycle 5 (Week 25) until EOT (Every 6 weeks)
BMS-986213 or nivolumab in combination with SOX	BMS-986213 (relatlimab 120 mg/nivolumab 360 mg) or nivolumab 360 mg	Day 1 and 22	Day 1 and 22	Day 1 and 22	Day 1 and 22	Day 1 and 22
	Oxaliplatin 130 mg/m ²	Days 1 and 22	Days 1 and 22	Days 1 and 22	Days 1 and 22	Days 1 and 22
	S-1 (tegafur/gimeracil/oteracil) (ie, 1 dose in the morning and 1 dose in the evening)	Days 1 to 14 and Days 22 to 35	Days 1 to 14 and Days 22 to 35	Days 1 to 14 and Days 22 to 35	Days 1 to 14 and Days 22 to 35	Days 1 to 14 and Days 22 to 35

7.1.5 Crossover for Investigator's Choice Chemotherapy

No crossover will be allowed among the XELOX, FOLFOX and SOX regimens in this study.

7.2 Method of Treatment Assignment

All participants will be centrally randomized using an Interactive Response Technology (IRT). Before the study is initiated, each user will receive log in information and directions on how to access the IRT. After the participant's initial eligibility is established and informed consent has been obtained, the participant must be enrolled into the study by using IRT to obtain the subject number. Every participant who signs the informed consent form must be assigned a subject number in IRT. The investigator or designee will register the participant for enrollment by following the enrollment procedures established by BMS. The following information is required for enrollment:

- Date that informed consent was obtained
- Year of birth
- Gender at birth

After enrollment in the IRT, participants who have met all eligibility criteria will be randomized through the IRT. The following information is required for participant randomization:

- Subject number
- Year of birth
- LAG-3 status ($\geq 1\%$ or $< 1\%$; no indeterminate allowed) provided by the central lab directly to the IRT system
- PD-L1 status (CPS < 1 or indeterminate, CPS ≥ 1 to < 5 , CPS ≥ 5) provided by the central lab directly to the IRT system
- Anatomical location (gastric vs GEJ)
- Region (Japan/Taiwan vs ROW)
- The choice of chemotherapy regimen - XELOX, SOX, or FOLFOX

The randomization procedures will be stratified by the following factors: LAG-3 expression ($\geq 1\%$ or $< 1\%$; no indeterminate allowed), Region (Japan/Taiwan vs ROW), and PD-L1 expression status (CPS < 1 and indeterminate, CPS ≥ 1 to < 5 , or CPS ≥ 5). The exact procedures for using the IRT will be detailed in the IRT manual.

Study treatment will be dispensed at the study visits as listed in Schedule of Activities ([Section 2](#)).

All participants will be enrolled using the IRT and will be designated a subject number after signing the Pre-Screen informed consent form (ICF). Per the ICF, information that identifies the participant, such as name, will be replaced with a unique code. The Sponsor refers to this coded information as Study Data. Personal information is coded to protect the participants' privacy. The participant's name and identifying information will remain with the study site and will remain confidential at all times.

7.3 Dosage Modification

7.3.1 Dose Modification Criteria for BMS-986213 or Nivolumab Plus Chemotherapy

If AEs are considered to be related to study treatment (BMS-986213 or nivolumab OR chemotherapy), every attempt must be made to attribute the individual study treatment to the AE, if possible, or to the combination regimen.

- For AEs that are deemed to be related to BMS-986213 or nivolumab ONLY by the treating physician, dose delays are permitted (see [Section 7.3.5](#)). Dose reductions are not permitted (see [Section 7.3.2](#)). The chemotherapy should continue as scheduled.
- For AEs that are deemed to be related to the chemotherapy ONLY by the treating physician, dose modifications are permitted according to local standard or local package insert (see [Sections 7.3.3.2](#) for XELOX, [7.3.3.3](#) for FOLFOX, and [7.3.3.4](#) for SOX). BMS-986213 or nivolumab administration should continue as scheduled.
- For AEs that are possibly related to the combination regimen (BMS-986213 or nivolumab PLUS chemotherapy), the most conservative toxicity management guidelines must be followed.
- If there is a delay in administration of study drug(s) due to toxicity, treatment with the other study agent(s) should continue as scheduled. Resumption of treatment should be at the next scheduled time point if criteria to resume treatment are met.

7.3.2 Dose Modification Criteria for BMS-986213 or Nivolumab

No dose reduction for BMS-986213 or nivolumab is permitted.

7.3.3 Dose Modification Criteria for Oxaliplatin-Plus-Fluoropyrimidine Treatment

Dose modifications of oxaliplatin, capecitabine, leucovorin, fluorouracil, and tegafur-gimeracil-oteracil are permitted according to local standards or local package inserts.

7.3.3.1 General Guidance for Dose Modification of Chemotherapy

- Treatment for the first cycle should only commence if all the inclusion criteria are met and the participant has been randomized. For subsequent cycles, dose delay/modification is permitted per local standard or as described in [Sections 7.3.3.2](#), [7.3.3.3](#), and [7.3.3.4](#).
- Doses of any study drug omitted for toxicity are not replaced or restored. Instead, the patient should resume the planned treatment cycles. Supportive care (for example, colony-stimulating factors [CSFs], blood and blood products, etc) can be administered in accordance with the latest American Society of Clinical Oncology or other equivalent guidelines.
- Dose modification, for nonserious and nonlife-threatening toxicities like alopecia, altered taste, or nail changes, may not be required and the final decision is left to the discretion of the treating investigator.
- In situations where concomitant toxicities of varying severity exist, dose modification will be tailored for the toxicity with highest CTCAE v5 grading.
- If there is a delay or modification in administration of one of the drugs in the chemotherapy regimen due to toxicity, treatment with the other drug(s) in the regimen should continue as

scheduled. If clinically appropriate, the investigator can delay all treatment components up to a maximum of 7 days to allow synchronized administration of all agents.

If toxicity related to any component of chemotherapy does not resolve in the same treatment cycle, the administration of that component can be delayed up to 6 weeks. If the toxicity does not resolve within 6 weeks, that component will be discontinued, unless it is determined by the treating investigator that the patient might benefit from continuation of the component.

7.3.3.2 Dose Modification Criteria for XELOX

Capecitabine

Toxicity due to capecitabine administration may be managed by symptomatic treatment and/or treatment interruption or dose reduction. Dose modifications of capecitabine are presented in Table 7.3.3.2-1. Once the dose has been reduced, it should not be increased at a later time. For those toxicities considered by the treating physician to be unlikely to become serious or life threatening (eg, alopecia, altered taste, or nail changes), treatment can be continued at the same dose without reduction or interruption. Participants taking capecitabine should be informed of the need to interrupt treatment immediately if moderate or severe toxicity occurs. Doses of capecitabine omitted for toxicity are not replaced.

Table 7.3.3.2-1: Recommended Dose Modifications of Capecitabine

Toxicity ^a	During a Course of Therapy	Dose Adjustment for Next Treatments (% of starting dose)
Grade 1	Maintain dose level	Maintain dose level
Grade 2		
1st appearance	Interrupt until resolved to Grade 0 to 1	100% (1000 mg/m ²)
2nd appearance		75% (750 mg/m ²)
3rd appearance		50% (500 mg/m ²)
4th appearance	Discontinue treatment permanently	-
Grade 3		
1st appearance	Interrupt until resolved to Grade 0 to 1	75% (750 mg/m ²)
2nd appearance		50% (500 mg/m ²)
3rd appearance	Discontinue treatment permanently	-
Grade 4		
1st appearance	Discontinue treatment permanently or, if physician deems it to be in the participant's best interest to continue, interrupt until resolved to Grade 0 to 1	50% (500 mg/m ²)

^a According to the National Cancer Institute of Canada Clinical Trial Group (NCIC CTG) Common Toxicity Criteria (version 1) or the Common Terminology Criteria for Adverse Events (CTCAE) of the Cancer Therapy Evaluation Program, US National Cancer Institute, version 4.0.

Oxaliplatin

Dose Modifications for Neurotoxicity

- For Grade 2 peripheral sensory neuropathy (moderate paresthesia or dysesthesia), or limiting instrumental activities of daily living, skip oxaliplatin. When toxicity resolves to \leq Grade 1, resume oxaliplatin at 75% of initial dose. If oxaliplatin is skipped for 4 weeks (2 consecutive doses) for neurologic toxicity, discontinue oxaliplatin.
- For Grade 3 or greater peripheral sensory neuropathy (severe paresthesia or dysesthesia), or limiting self-care activities of daily living, discontinue oxaliplatin.

Dose Modifications for Participants with Renal Impairment

- For normal renal function or mild to moderate renal impairment ($\text{CrCl} > 50 \text{ mL/min}$), the full dose of oxaliplatin can be administered.
- For severe renal impairment, the oxaliplatin dose should be reduced to 75% of the initial dose.

Dose Modifications for Participants with Hematological Toxicity

- For Grade 2 or Grade 3 thrombocytopenia, oxaliplatin should be reduced to 75% of the initial dose. For Grade 4 thrombocytopenia, the dose should be reduced to 50% of the initial dose.
- For Grade 3 or Grade 4 neutropenia or febrile neutropenia, the oxaliplatin dose should be reduced to 75% of the initial dose.

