7.1.2 Dose Schedule for BMS-986213 or Nivolumab Plus XELOX

Participants assigned to XELOX will receive BMS-986213 (relatlimab 120 mg/nivolumab 360 mg) or nivolumab 360 mg, administered IV over 60 minutes or 30 minutes, respectively, oxaliplatin 130 mg/m² administered IV on Days 1 and 22 of each 6-week treatment cycle, and

capecitabine 1000 mg/m² administered orally twice daily (ie, 1000 mg/m² in the morning and 1000 mg/m² in the evening) on Days 1 to 14 and Days 22 to 35 of each 6-week treatment cycle (see Table 7.1.2-1). Immunotherapy treatment should be administered first, prior to chemotherapy treatment. Dosing windows for subsequent XELOX doses should adhere to recommendations in the prescribing information or local standards, where indicated.

Premedication for potential infusion reaction is not recommended for the first dose of either treatment. Premedication maybe administered for nausea and vomiting prophylaxis, after the completion of the immunotherapy treatment or, in the absence of preceding immunotherapy, before chemotherapy administration, as clinical presentation warrants and per local standard.

Capecitabine should be taken with food.

Participants should be provided with drug diaries at each visit and instructed to record intake of capecitabine in the diary after each twice daily administration.

Table 7.1.2-1: Dose Schedule for BMS-986213 or Nivolumab Plus XELOX

Treatment Group	Drug Name	Cycle 1 (Week 1)	Cycle 2 (Week 7)	Cycle 3 (Week 13)	Cycle 4 (Week 19)	Cycle 5 (Week 25) until EOT (Every 6 weeks)
BMS-986213 or nivolumab in combination with XELOX	BMS-986213 (relatlimab 120 mg/nivolumab 360 mg), nivolumab 360 mg	Days 1 and 22	Days 1 and 22	Days 1 and 22	Days 1 and 22	Days 1 and 22
	Oxaliplatin 130 mg/m ²	Days 1 and 22	Days 1 and 22	Days 1 and 22	Days 1 and 22	Days 1 and 22
	Capecitabine 1000 mg/m ² twice daily (ie, 1000 mg/m ² in the morning and 1000 mg/m ² in the evening)	Days 1 to 14 and Days 22 to 35	Days 1 to 14 and Days 22 to 35	Days 1 to 14 and Days 22 to 35	Days 1 to 14 and Days 22 to 35	Days 1 to 14 and Days 22 to 35

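### The XELOX neuropathy rule restarts oxaliplatin at a share of the initial dose, so read literally it could raise a dose already halved for Grade 4 thrombocytopenia

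*Protocol*

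**What the plan says.** All places are in the protocol.

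- **Starting dose and schedule (7.1.2).** XELOX oxaliplatin is 130 mg/m², "administered IV on Days 1 and 22 of each 6-week treatment cycle".
- **Thrombocytopenia (7.3.3.2, oxaliplatin, hematological toxicity).** "For Grade 4 thrombocytopenia, the dose should be reduced to 50% of the initial dose".
- **Neuropathy (7.3.3.2, oxaliplatin, neurotoxicity).** Grade 2 sensory neuropathy means skipping oxaliplatin. Once it is back to Grade 1 or better, the site is to "resume oxaliplatin at 75% of initial dose". There is a limit on skipping: "If oxaliplatin is skipped for 4 weeks (2 consecutive doses) for neurologic toxicity, discontinue oxaliplatin".
- **Bar on increases.** The capecitabine paragraph of 7.3.3.2 says: "Once the dose has been reduced, it should not be increased at a later time". Section 7.3.3.4 gives SOX the same sentence, in a paragraph about reducing one or both agents, so SOX oxaliplatin is covered. The oxaliplatin part of 7.3.3.2 has no counterpart.
- **General guidance (7.3.3.1).** "In situations where concomitant toxicities of varying severity exist, dose modification will be tailored for the toxicity with highest CTCAE v5 grading". Also: "Doses of any study drug omitted for toxicity are not replaced or restored".
- **Alternative route (7.3.3).** Chemotherapy dose modifications "are permitted according to local standards or local package inserts". Sections 7.3.1 and 7.3.3.1 say much the same.

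**The concern.** The thrombocytopenia and neuropathy rules are both anchored to the initial dose. The thrombocytopenia rule is worded as a reduction and cannot naturally raise a dose. The neuropathy rule is worded as a restart at a fixed level, whatever the participant was receiving before. For someone at full dose it is a step down. For someone already at half dose it is, on its face, a step up that follows a second toxicity.

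What is at stake is the safety of a participant whose oxaliplatin was halved for Grade 4 thrombocytopenia. The protocol bars increases for SOX, where oxaliplatin has the same 130 mg/m² starting dose on the same days, and says nothing for XELOX. It gives no reason for the difference.

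**Working it through.** The protocol gives no mg/m² figures for reduced XELOX oxaliplatin, so there is no stated figure to reproduce. The doses follow from its percentages.

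**Dose arithmetic**

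- Initial dose (7.1.2): 130 mg/m².
- After Grade 4 thrombocytopenia (7.3.3.2): 0.50 × 130 = 65 mg/m².
- After resolved Grade 2 neuropathy (7.3.3.2): 0.75 × 130 = 97.5 mg/m².
- Change if the second rule is applied to a participant on 65 mg/m²: 97.5 − 65 = 32.5 mg/m², and 97.5 / 65 = 1.50, a rise of 50%.

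**Can the sequence occur within the skip limit?** Dosing on Days 1 and 22 of a 6-week cycle gives due dates on Days 1, 22, 43 and 64. I count from the date the first skipped dose was due.

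- One dose skipped (Day 22), restart on Day 43: 43 − 22 = 21 days. This is below 28 days and below two doses, so the restart rule applies.
- Two doses skipped (Days 22 and 43), next due on Day 64: 64 − 22 = 42 days and two doses, so oxaliplatin stops.

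On schedule, the restart rule therefore applies after exactly one skipped dose.

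**Does the participant stay on oxaliplatin after Grade 4 thrombocytopenia?** Section 7.3.4 stops treatment for Grade 3 or worse thrombocytopenia with clinically significant bleeding. It also stops the causative drug for a Grade 4 event that the investigator thinks unsuitable for dose reduction. Without bleeding, and with an investigator who chooses to reduce, oxaliplatin continues at 65 mg/m².

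**Does another rule block the increase?**

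- The highest-grade rule in 7.3.3.1 concerns toxicities present together. If the two overlapped it would point to the Grade 4 event and 50%. It does not reach toxicities that follow one another.
- The rule on omitted doses in 7.3.3.1 is about doses not given, not about the level at which dosing restarts.
- Section 7.3.1 requires the most cautious of the applicable rules when an event may be due to immunotherapy and chemotherapy together. It does not apply when the event is attributed to chemotherapy alone.
- Section 7.3.4 lists reasons to stop. It does not restrict increases.

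**Dose at restart, as written and with a lower-of rule, min(current dose, 97.5)**

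- Current 130: 97.5 as written; min(130, 97.5) = 97.5.
- Current 97.5: 97.5 as written; min(97.5, 97.5) = 97.5.
- Current 65: 97.5 as written; min(65, 97.5) = 65.

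Only the participant already at half dose is affected.

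**The case against.** The strongest reply is that nothing in the protocol orders the increase. Three parts of that reply stand.

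First, the dosing route is a choice. Sites may follow local standard or the package insert instead of 7.3.3.2, and either may forbid raising a reduced dose. Those texts are not in the documents. A reader might infer that the protocol compels 97.5 mg/m²; it does not, and could is the right word. The alternative route does not make the gap harmless, though. The same allowance covers capecitabine and S-1, and the protocol still writes out the bar for both.

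Second, the 50% instruction has no expiry or recovery clause. After the neuropathy resolves, both instructions can be said to apply and the text does not rank them. A careful investigator would probably stay at 65 mg/m². This makes the defect an unresolved conflict, not an order to escalate. But the neuropathy rule is the one addressed to the visit at which dosing restarts, and it names a level without reference to the current dose, so a literal reader has a reason to follow it.

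Third, section 7.3.7 treats thrombocytopenia and neurologic toxicity as events that can be related to the immunotherapy. Where the combination is a possible cause, 7.3.1 favours the cautious dose. The point is therefore confined to neuropathy attributed to chemotherapy alone.

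It is also fair to say that the chain of events is long, which limits how much weight the point can carry.

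**Conclusion.** The point holds as a low-severity gap in safety wording. Read literally, the XELOX neuropathy rule could raise oxaliplatin from 65 to 97.5 mg/m² (+50%). It rests on these conditions in turn: Grade 4 thrombocytopenia without clinically significant bleeding; an investigator who reduces instead of stopping; later Grade 2 neuropathy attributed to chemotherapy; recovery after one skipped dose; and a site that follows 7.3.3.2 as written. I take the sequence to be uncommon. The documents give no count or rate, so the number of participants affected cannot be stated.

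Three wider inferences are not supported:

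- **Bias between arms.** The rule is identical in both arms, and nothing in the documents links it to the response comparison, power or error rates.
- **The same increase under FOLFOX.** Section 7.3.3.3 also lacks the bar. Whether a participant on 50 mg/m² rises to 70 (70 − 50 = 20; 70 / 50 = 1.40, or +40%) depends on taking the neuropathy entry as the named level in Table 7.3.3.3-1. Taken as one level below the current dose, there is no increase.
- **A stopping rule in 7.3.4 that cannot operate.** That rule needs two earlier reductions for the same event, while 7.3.3.2 lists one oxaliplatin reduction for neutropenia and one for Grade 2 neuropathy. Local standard or the package insert may supply the second, and whether to list one is a clinical choice, not an error.

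**What to change.** In the XELOX neurotoxicity rule of 7.3.3.2, have oxaliplatin restart at the lower of the current dose and 75% of the initial dose. The intended step for participants at full dose is kept.

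Do not copy the general no-increase sentence into the XELOX oxaliplatin text. It would also cover the 75% reduction for severe renal impairment, and would then conflict with the statement in the same section that the full dose can be given when creatinine clearance is above 50 mL/min. Whether to raise the dose again after renal recovery is a clinical question that this point does not need to settle. The other oxaliplatin rules in the section are framed as reductions or as permission for the full dose, so only the restart clause needs to change.

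The cost is one clause in the protocol and a communication to sites. Data collection and analysis are unaffected. I would class it as a free improvement for patient safety.
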